4.8 Determination of Sample Size

The Phase 2 portion of the study will accrue 30 patients. Any patients in screening at the time that the 30th patient is enrolled will be permitted to enroll, should they be eligible. This sample size is based on a Simon's 2-stage design where the Phase 2 portion of the study may be stopped if none of the first 10 treated patients have a response. The hypothesized response rate of a poor drug is 5%, while the hypothesized response rate of a good drug would be at least 20%. Using a 1-sided alpha of 0.05 and power of 80%, if at least 1 of the first 10 patients has a response, the Simon's design recommends accruing up to at least 29 total patients to test the null hypothesis. The probability of stopping early is 59.9% with a type I error rate of 0.0468.

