3.2. Phase 2 (Dose Expansion)

3.2.1. Phase 2 Sample Size

The Phase 2 portion of the study will accrue 30 patients. Any patients in screening at the time that the 30th patient is enrolled will be permitted to enroll, should they be eligible. This sample size is based on a Simon's 2-stage design where the Phase 2 portion of the study may be stopped if none of the first 10 treated patients have a response. The hypothesized response rate of a poor drug is 5%, while the hypothesized response rate of a good drug would be at least 20%. Using a 1-sided alpha of 0.05 and power of 80%, if at least 1 of the first 10 patients has a response, the Simon's design recommends accruing up to at least 29 total subjects to test the null hypothesis. The probability of stopping early is 59.9% with a type I error rate of 0.0468 (<http://cancer.unc.edu/biostatistics/program/ivanova/SimonsTwoStageDesign.aspx>).

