3. INVESTIGATIONAL PLAN

3.1 Overall Study Design

This is an open-label, 2-part, Phase 1b/2 study of nanatinostat and valganciclovir for the treatment of patients with relapsed/refractory, pathologically confirmed EBV–positive (EBV⁺) lymphoid malignancies or lymphoproliferative diseases regardless of histologic subtype.

The study will be conducted at approximately 30 sites in the US and Brazil. Written informed consent in a language fully comprehensible to the prospective patient will be obtained from each patient prior to performing any study-related procedures.

The Phase 1b portion of the study will evaluate safety and define an RP2D using a modified 3+3 design for oncology studies in patients with EBV⁺ lymphomas ([Section 3.1.1](#)). The Phase 2 portion of the study will evaluate the RP2D in patients with EBV-associated lymphomas or lymphoproliferative disease, using a Simon’s 2-stage design to allow for early stopping for futility ([Section 3.1.2](#)). The study defines a cycle length as 28 days.

Safety assessments will make use of all available data including using adverse event, clinical laboratory parameters, vital signs, electrocardiograms (ECGs), physical exams, and performance status (PS) assessments.

Response will be assessed locally using a combination of physical exam and imaging (e.g. PET-CT scan, CT scan, MRI, bone marrow/aspirate) as appropriate for each patient. Response assessments will be performed at least every two cycles, with an initial assessment after Cycle 2, using imaging modalities appropriate for the patients’ specific lymphoma based on the Recommendations for Initial Evaluation, Staging, and Response Assessment of Hodgkin and Non-Hodgkin Lymphoma: the Lugano Classification ([Cheson et al., 2014](#)).

A PK assessment of both nanatinostat and valganciclovir will be performed predose, at various timepoints following the first administration of nanatinostat/valganciclovir, and at additional timepoints within the first two cycles for all patients. A detailed schedule

that describes the coordination of PK sampling and ECGs is provided in Table 14 of the clinical study protocol.

Survival and follow-up assessments will be conducted at least every 3 months for assessment of additional therapy, response status, and survival following the safety follow-up assessment.

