No formal statistical analysis will be performed to compare cohorts. This study is exploratory in nature; descriptive statistics will be tabulated by study phase and cohort and reviewed to evaluate all study endpoints.

4.1.2 *Summarization by Visit*

In general, data summarized by study visit will be based on the nominal, scheduled visit label as reported on the eCRF. Data collected for the last patient visit will be summarized separately and this summary will be labeled as “End of Treatment” in the analysis.

For laboratory data summaries, data summarized by study visit will be based on the nominal, scheduled visit label as reported on the eCRF when available. If the scheduled visit is not available, then all data collection, including unscheduled and early

termination visits, will be reassigned a study visit based on the actual days relative to baseline using the visit windows identified in [Table 3](#) below.

Table 3 Visit Windows for Analysis

Scheduled Visit	Target Study Day	Study Day Interval
Baseline	0	≤ 0
Cycle 1 Day 1	1	1
Cycle 1 Day 2*	2	2
Cycle 1 Day 8	8	3 – 11
Cycle 1 Day 15	15	12 – 18
Cycle 1 Day 22	22	19 – XX^{**}
Cycle 2 Day 1	$XX + 1$	$XX + 1$
Cycle 2 Day 8	$XX + 8$	$(XX + 2) – (XX + 11)$
<hr/>		
...		

*Note Cycle 1 is the only cycle with a schedule Day 2 visit

** Day 22 is the last scheduled visit within each cycle, and the end of the study interval (XX) is calculated as the day before the start of the subsequent cycle.

If more than one value is mapped to the same visit, the value collected closest to the target study day will be considered for summarization. If two values collected on different days are mapped to the same scheduled visit and are equidistant from the target study day, the earlier of the values will be considered. The visit displayed on subject data listings will be reflective of the scheduled visit label as reported on the eCRF. Study days relative to baseline will be displayed for each visit to indicate to which visit the assessment may have been reassigned, if any.

Otherwise, data collected at unscheduled visits will not be included in by-visit summaries but will be considered when endpoint derivations potentially include multiple visits (e.g., determination of baseline value, determination of worst post-baseline value, etc.). All data will be included in patient listings.

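### The SAP gives conflicting denominators for the primary ORR, and its Simon error rates belong to a 29-patient reference design and a test that is not planned

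*SAP*

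**What the plan says.** **ORR denominator.** SAP 3.4.2.1 defines the primary efficacy endpoint as a proportion of patients and names no analysis set. The set comes from elsewhere:

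- SAP 4.6.1 and 4.6.5.6 put every efficacy summary on the EES.
- SAP 4.2 admits a patient to the EES only if all eligibility criteria are met and a minimum of one evaluable post-baseline tumour assessment exists.
- Protocol 12.1 has a similar efficacy dataset but asks only for a post-baseline assessment, without the qualifier that it be evaluable.
- SAP 4.6.5.2 bases best overall response on patients with baseline and post-baseline data. Its next sentence treats non-evaluable patients as non-responders and keeps them in the denominator.
- Protocol 3.18 and SAP 3.1.2 allow Phase 2 patients without a disease assessment to be replaced. Table 4 in SAP 4.6.5.2 has a row for death before the first assessment.

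**Simon design.** Protocol 3.2.1 and SAP 4.8 use a 5% versus 20% response rate, one-sided alpha 0.05 and 80% power. The trial "may be stopped if none of the first 10 treated patients have a response". If it continues, the protocol speaks of "accruing up to at least 29 total subjects to test the null hypothesis", and the SAP likewise of "accruing up to at least 29 total patients to test the null hypothesis". Both give the same operating characteristics: "The probability of stopping early is 59.9% with a type I error rate of 0.0468". Planned accrual is different: "The Phase 2 portion of the study will accrue 30 patients", and "Any patients in screening at the time that the 30th patient is enrolled will be permitted to enroll" if eligible. Neither document states a final cut-off. SAP 3.1 gives the purpose of the design as "to allow for early stopping for futility". SAP 4.1.1 adds "This study is exploratory in nature", SAP 4.6.5.5 rules out hypothesis tests, and Protocol 12.2 plans descriptive statistics with exact 95% intervals.

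**The concern.** ORR is the primary efficacy endpoint, and two programmers following this SAP could report different values from the same data. The difference has a known direction. A patient who was never assessed cannot be a responder, so removing that patient shrinks the denominator and leaves the numerator alone. Such patients can include early deaths, and replacement means they need not reduce the number of evaluable patients.

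The Simon paragraph is a smaller matter. It attaches a type I error and a power to Phase 2 that belong to another sample size, an unstated cut-off and a test that the analysis sections do not contain. A reader of the study report could take 0.0468 as the error rate of a decision that is never made.

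**Working it through.** **1. Denominator: the rules side by side**

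| Patient | EES rule (SAP 4.2, 4.6.1, 4.6.5.6) | Non-evaluable rule (SAP 4.6.5.2) |
|---|---|---|
| Treated, no post-baseline assessment | Out | In, as non-responder |
| Treated, assessed, result not evaluable | Out (in under the Protocol 12.1 wording, if its other conditions are met) | In, as non-responder |
| Treated, evaluable, failed an entry criterion | Out | Not addressed |

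For a patient with no evaluable assessment at all, the two rules cannot both be followed.

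Size, for 30 treated patients and 6 responders. The documents give no unassessed rate, so 10% and 20% are assumptions:

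- none left out: 6/30 = 20.0%
- 10% unassessed: 30 − 3 = 27, and 6/27 = 22.2%
- 20% unassessed: 30 − 6 = 24, and 6/24 = 25.0%

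**2. Simon design: reproducing the plan's figures**

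Inputs (Protocol 3.2.1, SAP 4.8): p0 = 0.05, p1 = 0.20, stage 1 of 10 patients, stop at 0 responses, total N = 29. The final cut-off c is not given. A search for the optimal Simon design with these inputs returns 10 then 29 patients, with rejection at c = 4 or more responses.

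Probability of stopping early at p0: 0.95^10 = 0.5987, which is the stated 59.9%.

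With the stop enforced,

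P(reject) = Σ over x = 1 to 10 of P(X1 = x) × P(X2 ≥ c − x), where X1 ~ Bin(10, p) and X2 ~ Bin(N − 10, p).

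For N = 29 and c = 4:

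| Stage 1 responses | At p = 0.05 | At p = 0.20 |
|---|---|---|
| 1 | 0.3151 × 0.0665 = 0.0210 | 0.2684 × 0.7631 = 0.2048 |
| 2 | 0.0746 × 0.2453 = 0.0183 | 0.3020 × 0.9171 = 0.2770 |
| 3 | 0.0105 × 0.6226 = 0.0065 | 0.2013 × 0.9856 = 0.1984 |
| 4 or more | 0.0010 | 0.1209 |
| Sum | 0.0468 | 0.8011 |

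Both stated figures are reproduced.

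**3. The same formula at the planned size (stop enforced; alpha / power)**

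| N | At least 4 responders | At least 5 responders |
|---|---|---|
| 29 | 0.0468 / 80.1% | 0.0124 / 68.1% |
| 30 | 0.0513 / 81.4% | 0.0141 / 70.5% |
| 32 | 0.0605 / 83.5% | 0.0179 / 74.7% |
| 35 | 0.0753 / 85.7% | 0.0247 / 79.4% |

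From N = 30 to 35 no cut-off meets both alpha 0.05 and 80% power. Sizes above 30 are shown because enrolment from screening has no cap. The stop is also worded as optional. If it were not applied, at least 4 of 30 would have alpha 0.0608, and more at larger N.

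**The case against.** On the denominator, the best defence is that the non-evaluable rule does have a use under Protocol 12.1. A patient who was scanned but whose result could not be evaluated is in the protocol's set and would count as a failure. That is fair for the protocol's wording. The SAP's set, which governs the analysis, requires an evaluable assessment, so the conflict stands and the two definitions also differ from each other. The SAP does make the exclusions visible: 4.6.1 lists each patient left out with the reason, and 4.3.1 tabulates the size of each set. This lets a reader rebuild the other ORR but does not say which is primary.

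On the Simon figures, the defence is stronger. The text attributes 29 to the Simon design and states accrual of 30 separately. The figures are right for the design named, one extra patient moves alpha only from 0.0468 to 0.0513 with power rising, and a missing cut-off affects no planned analysis when no test is planned. All of this stands.

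A reader might also infer two stronger points that the documents do not support:

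- That the SAP dropped a test and failed to list it in SAP 4.9. Protocol 12.2 already plans descriptive statistics only, so the SAP changed nothing here. The testing phrase is loose wording shared by both sample-size paragraphs.
- That replacing unassessed patients inflates the type I error by a calculable amount. Such a figure needs unassessed rates and a mixed counting rule found in neither document, applied to a test that is not planned. It also vanishes if the 5% null refers to evaluable patients.

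**Conclusion.** The denominator conflict is real and should be settled before the analysis. Under the SAP's own definitions the EES-based ORR omits patients whom SAP 4.6.5.2 says to count, and leaving out unassessed patients can only keep or raise the result. In the illustration the rise is 2.2 to 5.0 percentage points, which rests on assumed unassessed shares of 10% and 20%. The actual size depends on how many treated patients lack an evaluable assessment.

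The Simon point is a wording matter. The quoted error rates are not wrong. They describe 0/10 with the stop enforced, then at least 4 of 29. They do not describe 30 or more patients, and no planned test uses them. The recomputed figures assume independent responses at exactly 5% or 20% and an enforced stop.

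**What to change.** **Primary ORR (SAP 4.2, 4.6.1, 4.6.5.2, 4.6.5.6).**

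1. State one denominator: all treated Phase 2 patients, with anyone lacking an evaluable post-baseline assessment, including any patient who was replaced, counted as a non-responder.
2. Show the EES ORR as supportive.
3. Say openly that the new denominator also brings in treated patients who failed an entry criterion. Their effect could go either way.
4. List the choice in SAP 4.9 as a difference from Protocol 12.1, and disclose that it was made late in an open-label trial.

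**Simon paragraph (SAP 4.8).** Replace the last two sentences with text to this effect: the Simon design is the futility rule and the sample-size rationale; no test of ORR is planned; the early-stopping probability of 59.9%, type I error of 0.0468 and power of 80% belong to the 29-patient reference design (0/10 with the stop applied, then at least 4 of 29); at 30 patients the type I error and power are 0.0513 and 81.4% for at least 4 responders, and 0.0141 and 70.5% for at least 5; they change further with each patient enrolled from screening (for at least 4, alpha 0.0605 at 32 and 0.0753 at 35). SAP 4.9 needs no entry on testing.

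**Cost.** Wording in five SAP sections and one entry in SAP 4.9. No protocol amendment, extra patients or new data are needed. The downside is a possibly lower reported ORR.

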4.9 Changes in the Conduct of the Study or Planned Analyses

The following changes to planned analyses identified within the development of this SAP, relative to the descriptions provided within the clinical study protocol are listed below:

- Section 3.1.3 of the protocol includes a table for intended Phase 1b Cohort Doses.
 - The original intended Valganciclovir dose for Cohort 1 was 900 mg BID, but this was modified per the SRC recommendation after the first

4 patients. The actual Valganciclovir dosing was 900 mg BID for the first 4 patients and then 450 mg BID for the last 3 patients.

- The original intended Nanatinostat dose for Cohort 3 was 20 mg QD. The SRC later recommended to revise this dose to 20 mg QD 4 days per week following review of Cohort 1 safety data.
- Section 3.8 of the protocol states that a central review of patient scans will be performed and may include an assessment based on both Lugano and RECIL criteria. This central review was not performed.
- Section 6.4.1 of the protocol describes urine PK sample collection and, but this was not collected and will not be analyzed.

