12.3. Analysis of the Primary Endpoints

12.3.1. Safety Profile

The safety dataset will be used for all the safety summaries.

The incidence of all AEs will be tabulated by dose received. These AEs will be classified by System Organ Class and preferred term using the Medical Dictionary for Regulatory Activities (MedDRA).

For incidence reporting, if a patient reported more than 1 AE that was coded to the same System Organ Class or Preferred Term, the patient will be counted only once at the highest observed grade for that specific system organ class or preferred term.

An overview of AEs, which includes patient incidence of AEs, AEs by severity, SAEs, deaths, and AEs leading to discontinuation, will be presented.

A summary of the number DLTs per cohort will be provided.

Serious adverse events will be listed and summarized in a similar manner to AEs.

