3.1.1 Phase 1b (Dose Escalation)

During the dose escalation portion of the study, dosing will be based on assigned cohort. Approximately 25 patients are expected to enroll in this phase. Cohort size will be up to 7 patients using a conventional modified 3+3 design for dose escalation studies in oncology.

On Cycle 1 Day 1, in an effort to ensure that patients tolerate oral valganciclovir prior to receiving nanatinostat, valganciclovir will be taken first, followed by nanatinostat approximately 1 hour later. For all subsequent administrations, the sequence of nanatinostat and valganciclovir can be dictated by patient convenience (e.g., both drugs may be taken together if tolerated by the patient). With the implementation of Protocol Amendment 4.0, nanatinostat and valganciclovir will be taken together at all timepoints, including Cycle 1 Day 1.

The first cycle is defined as the dose-limiting toxicity (DLT) assessment period. Grading of DLTs will be according to the National Cancer Institute Common Terminology Criteria for Adverse Events (NCI CTCAE) version 5 and detailed in Section 3.1.5 of the protocol as well as [Section 3.4.1](#) of the SAP. Patients who are unable to complete the DLT assessment period for reasons other than study drug-related toxicity may be replaced if needed to achieve at least 3 patients evaluable for DLTs.

A Safety Review Committee (SRC) comprised of study investigators, the study medical monitor and a Sponsor representative will govern the conduct of the study, and will have the option of defining additional cohorts and doses either below, above, or intermediate to the planned doses as needed based on data generated from prior cohorts. The SRC may also modify the dosing schedule for either nanatinostat or valganciclovir as required to accommodate different dosage strengths and patient convenience. However, when the schedule is adjusted, the total daily dose will remain unchanged. The Phase 1b planned doses for each cohort are provided in Table 2.

Table 2 Phase 1b Dose Levels by Cohort

Cohort Number	Dose Nanatinostat	Dose Valganciclovir
1	10 mg BID (20 mg daily dose)	900 mg BID
2a	5 mg BID (10 mg daily dose)	450 mg BID
2b	10 mg QD (10 mg daily dose)	450 mg BID

Cohort Number	Dose Nanatinostat	Dose Valganciclovir
2c	10 mg QD (10 mg daily dose)	900 mg QD
3	20 mg QD (20 mg daily dose), 4 days on and 3 days off in a 7-day regimen	900 mg QD

BID, twice daily; QD, once daily.

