4.1.1 Reporting Conventions

Tables and figures will be summarized by cohort and study phase. Tables will also include a column for all patients who receive the capsule formulation. In general, all data collected, and any derived data will be presented in patient data listings, for all enrolled patients. Listings will be ordered by site, study phase, patient number, cohort,

and assessment or event date. The cohort presented in listings will be based on the planned assignment, unless otherwise noted.

Summaries will be based on patient data from both the dose escalation and dose expansion phases up until the time when the final dose escalation patient has completed at least 12 months of follow-up from their first disease response assessment after two cycles of therapy, or until all patients have discontinued the study, died, withdrawn consent, discontinued, or are lost to follow-up, whichever occurs first.

In general, continuous variables will be summarized to indicate the study population sample size (N), number of patients with available data (n), mean, SD, median, minimum, and maximum values. Categorical variables will be summarized by the population size (N), number of patients with available data (n), number of patients in each category, and the percentage of patients in each category. Unless otherwise noted, the denominator to determine the percentage of patients in each category will be based on the number of patients with available data. Select ordinal data may be summarized using both descriptive statistics and counts and percentages of patients in each category, as appropriate.

Non-zero percentages will be rounded to one decimal place. Rounding conventions for presentation of summary statistics will be based on the precision of the variable of summarization, as it is collected in its rawest form (i.e., on the electronic case report form [eCRF] or as provided within an external file) and are outlined as follows:

- The mean and median will be rounded to one more decimal place than the precision of the variable of summarization.
- Measures of variability (e.g., SD, SE) will be rounded to two more decimal places than the precision of the variable of summarization.
- Minimum and maximum values will be presented using the same precision as the variable of summarization.

Other statistics (e.g., CIs) will be presented using the same general rules outlined above or assessed for the most appropriate presentation based on the underlying data.

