4.5.2 Adverse Events

Treatment-emergent adverse events (TEAEs) are defined as those adverse events (AEs) with onset after the first dose of study drug or pre-existing events that worsened by at least one grade after the first dose during the study. Treatment-emergent AEs will be summarized by study phase and cohort. Events reported with a partial onset date (e.g., month and year are reported but the day is missing) will be considered to be treatment-emergent if it cannot be confirmed that the event onset was prior to the first dose of study drug based on the available date entries.

Verbatim terms on case report forms will be mapped to preferred terms and system organ classes using the Medical Dictionary for Regulatory Activities (MedDRA, version 25.0). As an additional safety analysis, certain hematological AEs will be programmatically re-mapped to preferred terms and system organ classes consistent with CTCAE v5.0 categories. Select AE summaries will be repeated using this alternative mapping.

Summaries that are displayed by system organ class and preferred terms will be ordered by descending incidence of system organ class and preferred term within each system organ class. Summaries displayed by preferred term only will be ordered by descending incidence of preferred term. Summaries of the following types will be presented:

- Overall summary of number of unique TEAEs and patient incidence of TEAEs meeting various criteria.
- Overall summary of number of unique SAEs and patient incidence of SAEs meeting various criteria
- Patient incidence of TEAEs by MedDRA system organ class and preferred term
- Patient incidence of TEAEs by CTCAE toxicity grade, MedDRA system organ class, and preferred term.
- Patient incidence of dose-limiting toxicity AEs by MedDRA system organ class and preferred term.
- Patient incidence of TEAEs leading to dose interruption, reduction or discontinuation of valganciclovir by MedDRA system organ class and preferred term.
- Patient incidence of TEAEs leading to reduction or interruption of nanatinostat and valganciclovir by system organ class and preferred term
- Patient incidence of TEAEs leading to discontinuation of nanatinostat and valganciclovir by system organ class and preferred term

- Patient incidence of SAEs by MedDRA system organ class and preferred term.
- Patient incidence of SAEs by CTCAE toxicity grade, MedDRA system organ class, and preferred term.

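### SAP 4.9 reports two valganciclovir doses in Cohort 1, but the SAP tabulates AEs by cohort instead of by dose received as Protocol 12.3.1 requires

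*SAP*

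**What the plan says.** SAP 4.9 records a change made during Cohort 1 on the recommendation of the Safety Review Committee. "The original intended Valganciclovir dose for Cohort 1 was 900 mg BID", but after the first four patients it was modified: "The actual Valganciclovir dosing was 900 mg BID for the first 4 patients and then 450 mg BID for the last 3 patients". No change to nanatinostat is reported for this cohort, so it stands at the 10 mg BID of SAP Table 2 throughout. Table 2 shows only 900 mg BID of valganciclovir for Cohort 1.

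The SAP's general grouping rule (4.1.1) is "Tables and figures will be summarized by cohort and study phase". For listings the same section says "The cohort presented in listings will be based on the planned assignment, unless otherwise noted". For AEs, SAP 4.5.2 repeats the rule: "Treatment-emergent AEs will be summarized by study phase and cohort". SAP 4.5.1 (exposure) and 4.5.4 (laboratory data) group in the same way. SAP 4.7.2 and 4.7.3 summarise PK concentrations and parameters by treatment, a term that the SAP does not define for this purpose.

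Protocol 12.3.1 says of AEs: "The incidence of all AEs will be tabulated by dose received". The same section plans the DLT summary per cohort.

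**The concern.** Safety and tolerability is a primary objective, and the AE tables are its main output. Valganciclovir dose bears on them. Protocol 1.9 names hematologic toxicity and acute renal failure among the drug's significant AEs, Protocol 1.10 allows a modified dose to manage its known AEs, and Protocol 1.12.1 lists thrombocytopenia and renal dysfunction as toxicities shared with nanatinostat. A reader who takes the Cohort 1 column to describe the regimen in Table 2 would be reading a blend in which three of seven patients had half that valganciclovir dose.

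Cohort 1 also fed later decisions: SAP 4.9 says the Cohort 3 nanatinostat schedule was revised after review of Cohort 1 safety data.

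Finally, SAP 1 undertakes to explain any difference between the protocol's statistical methods and its own. The move from dose received to cohort for AEs is such a difference, and it is not explained.

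**Working it through.** The plan states no figure on this point to reproduce. The check compares the grouping rules and then works out what pooling would do to simple summaries.

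**1. Dose actually given.** From SAP 4.9: 4 patients at 900 mg BID (1800 mg/day) and 3 at 450 mg BID (900 mg/day). 4 + 3 = 7, which fits the stated maximum: "Cohort size will be up to 7 patients using a conventional modified 3+3 design". The dose ratio is 1800/900 = 2. This is a change in total daily dose, so it is not covered by the schedule adjustments in SAP 3.1.1, which keep the daily dose unchanged.

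**2. Match to Table 2.** The last three patients had nanatinostat 10 mg BID with valganciclovir 450 mg BID. Row 1 has 900 mg BID of valganciclovir. Rows 2a and 2b have 450 mg BID, but with half the daily nanatinostat dose. Rows 2c and 3 have 900 mg QD. No row of Table 2 describes this regimen.

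**3. Grouping rule by output.**

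| Output | Protocol | SAP |
|---|---|---|
| AEs | dose received (12.3.1) | phase and cohort (4.5.2) |
| DLTs | per cohort (12.3.1) | cohort, by the default in 4.1.1 |
| Exposure | not specified separately | phase and cohort (4.5.1) |
| Laboratory | by cohort and phase for continuous variables (12.2) | phase and cohort (4.5.4) |
| PK | descriptive, for all Phase 1b cohorts (12.4.1) | by treatment, undefined (4.7.2, 4.7.3) |

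Only the AE row is a conflict between the documents. None of the changes listed in SAP 4.9 mentions it.

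**4. Effect on a DLT proportion (illustration; no counts are given).** Take one DLT in the cohort. Exact 95% limits are Beta(0.025; x, n−x+1) and Beta(0.975; x+1, n−x), with a lower limit of 0 when x = 0.

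| Display | Proportion | Exact 95% CI |
|---|---|---|
| Pooled | 1/7 = 14.3% | 0.4–57.9% |
| DLT at 900 mg BID | 1/4 = 25.0% | 0.6–80.6% |
| other group | 0/3 | 0–70.8% |
| DLT at 450 mg BID | 1/3 = 33.3% | 0.8–90.6% |
| other group | 0/4 | 0–60.2% |

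Protocol 3.1.7 defines the MTD by at most 1 DLT among 6 or 7 patients. A pooled 1/7 would look as if it met that definition, yet neither regimen was given to 6 patients.

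**5. Effect on ganciclovir PK, if it is pooled.** Assume exposure is proportional to dose and set the 450 mg mean to 1 and the 900 mg mean to 2. The pooled arithmetic mean is (4×2 + 3×1)/7 = 11/7 = 1.571. That is 157% of the 450 mg value and 1.571/2 = 79% of the 900 mg value. The pooled geometric mean is 2^(4/7) = 1.486, which is 149% and 74% respectively.

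**The case against.** The strongest reply is that the change is disclosed, the analysis is descriptive with no formal comparison of cohorts (SAP 4.1.1), and the recommended Phase 2 dose is already fixed in SAP 3.3.1.1. Splitting seven patients into four and three gives very wide intervals. Individual valganciclovir doses can also differ within any cohort under the renal and tolerance rules of Protocol 5.2.3, so two columns do not fully deliver dose received. All of this is fair. It limits the consequences, but it does not reconcile the AE grouping with Protocol 12.3.1 or explain why the departure is unlisted.

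A reader might also infer more than the documents support:

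- **That pooling hides a breach of the MTD rule.** Two DLTs in the first four would be 50%, shown as 2/7 = 28.6%, below 33%. But under Protocol 3.1.4 expansion follows one DLT in the first 3 or 4, and two or more in an expanded cohort exceed the MTD by count; Protocol 3.1.7 likewise reads its 33% as at most 1 of 6 or 7. So 2/7 would already exceed it.
- **That the DLT summary departs from the protocol.** It does not; per cohort is the protocol's own plan. The difficulty there is only that the cohort is mixed.
- **That ganciclovir PK is pooled.** SAP 4.7 does not say so. Two valganciclovir doses could be two treatments. Apparent clearance is also divided through by dose, so it would not be distorted in the same way.
- **That three patients are mislabelled in listings.** They were Cohort 1 patients, so the cohort label is correct, and the table and listing templates are not among the documents.
- **That the dose was changed because of toxicity.** SAP 4.9 gives no reason for the Cohort 1 change.
- **That the pooled results describe no dose given.** Both doses were given; the column is a mixture of two real regimens.

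**Conclusion.** The point holds in a bounded form. As written, the SAP yields a Cohort 1 AE column that mixes two regimens with a two-fold difference in valganciclovir dose, under a cohort that Table 2 defines by the higher dose alone. For AEs this contradicts Protocol 12.3.1, and SAP 4.9 does not list it. Exposure and laboratory summaries carry the same mixture without contradicting the protocol. For ganciclovir PK the finding is ambiguity, not pooling.

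The textual conflict and the 4/3 split rest on no assumption. The sizes do: the DLT figures suppose one event, and the PK figures suppose both pooling and dose-proportional exposure. The repair is cheap and should be made before the tables are produced. No view is taken on which dose is right.

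**What to change.** - In the AE, DLT and exposure tables, show Cohort 1 as two columns by valganciclovir dose received (n = 4 and n = 3). A combined column may stay if it is marked as mixed. Laboratory tables can remain by cohort with the same mark.
- In SAP 4.7, define treatment as the dose received, so that ganciclovir PK is split in the same way.
- Show each patient's actual valganciclovir dose in the listings beside the planned cohort. This also covers individual reductions.
- Footnote SAP Table 2 with the two doses given in Cohort 1.
- Bring SAP 4.5.2 into line with Protocol 12.3.1, or list the departure and its reason in SAP 4.9.

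The cost is one extra column and a few sentences. The drawback is small columns with wide intervals, which is a fair picture of how little was observed at each dose.
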